#### **Adverse event (AE) / adverse reaction (AR) expectedness criteria**

AE/AR is considered unexpected, if its nature, seriousness or outcome does not correspond with the Reference safety document (there must be ONLY ONE Reference safety document defined by the Protocol, and Clinical trial appendices; it should be referred to in the protocol and appendix cover letters).

If the product has already been issued a registration certificate (RC), the Reference safety document is the Summary of product characteristics (SPC). If there are multiple versions of the SPC (e.g., if there are national product RCs), the most appropriate version of the SPC should be provided.

If the product has never been issued with a registration certificate, the Reference safety document is the Investigator's Brochure (IB).

### **8.3 Suspected unexpected serious adverse reaction (SUSAR)**

Any serious unexpected adverse events, considered by an Investigator or Sponsor as associated with the product are qualified as unexpected AR (SUSAR). SUSARs should be reported according to the instructions in Section 8.4.

### **8.4 Adverse events monitoring and reporting**

At each study visit, the investigator will assess any subjective or objective AEs. AEs identified based on complaints of a patient, patient's relatives/legal representatives, over phone, in writing or by e-mail will also be documented. In such cases, the investigator should try to assess the AE and obtain medical conformation.

In case of AE, the investigator must document the AE in the special CRF section "Adverse event form"; a new page should be used for every AE, the investigator should assess causal relationship of the AE and the product regardless of whether the AE is serious or not, whether it is associated with the drug, discovered by the investigator or patient.

All available information and results of diagnostic procedures (laboratory, instrumental tests, etc.) should be documented and/or attached to the CRF.

The investigator must monitor SAE for the entire study duration (including the follow-up period) until the outcome.

The investigator must monitor cases of pregnancies that occurred while on treatment with the investigated treatment or during follow-up period and document any congenital abnormalities.

### **Reporting requirements**

The investigator must report SAEs (both related and unrelated to the investigated product) by faxing the CRF Adverse Event Form pages **no later than 24 hours** after he/she became aware of the SAE:

If safety issues are dealt with directly by Sponsor:

Sponsor medical expert [name],  
[contact], mob. [name]  
[contact]

All serious adverse events must be monitored until the outcome.

Any information and required documents that may be available (copies of results of laboratory tests, procedures, autopsy, cause of death data, etc.) will be provided by the Investigator by means of separate written reports directly to the Sponsor medical expert as soon as possible.

The investigator should comply with applicable local regulations for AR reporting to regulatory authorities/ethics committees.

### **8.5 Sponsor responsibilities for AE reporting**

The sponsor should ensure that all necessary information about suspected serious and suspected unexpected serious adverse reactions (SUSAR) is duly reported to the regulatory authorities and to Ethics Committees within the appropriate time period after the sponsor became aware of the event (the day when the Sponsor received a SUSAR report):

- fatal and life-threatening unexpected events - not later than 7 days;
- other unexpected serious events - not later than 15 days.

The sponsor should ensure that in case any further information about the event becomes available, all the required data and supporting documents (which may become available in the future) is also duly reported within the time period specified above.

## **9 DATA MANAGEMENT AND RECORD-KEEPING**

### **9.1 Data collection and processing**

The investigator must fill out Case Report Forms (CRFs) according to the instructions obtained before the start of the study. Paper CRF will be used in the study. The investigator must store a copy of a CRF along with other study documents in a place with restricted access. All data documented in CRFs must be supported by the data in the patient source documents.

CRF data will be entered into the integrated database by authorized personnel in accordance with internal Sponsor SOPs. Double data entry will be employed. All data will be systematically analyzed for errors and inaccuracies. Data that need clarification is entered into special forms and sent to the site for clarification. After questionable data is clarified, copies of the signed forms must be stored in the CRF and the originals must be provided to the data managing staff.

The database will be locked after all questionable data are verified, and it is confirmed that the entered data are complete and accurate.

Statistical analysis will be conducted under the supervision of a responsible biostatistician according to prespecified statistical analysis plan (please refer to “Statistical analysis”).

### **9.2 Data recording**

The investigator is required to maintain source documents for every study participant, containing demographic and medical data, including results of protocol-specified investigations. All information contained in CRFs should match the source documents. The investigator must fill out a CRF based on patient's medical record and should store the study documents, including informed consent form, the protocol, the investigator's brochure, and all protocol amendments in a room with restricted access.

### **9.3 Archiving**

The investigator must ensure appropriate documentation storage for at least 15 years after the end of the study. Disposal of the study documents is possible with the Sponsor written permission. The sponsor should inform the investigator in writing about the expiration of the documentation storage term.

Key documents (that allow evaluating the study conduct and quality of the data obtained) should be stored in a way that ensures their integrity and complete security for the entire storage term, and also guaranties their availability on request from competent authorities.

The key documents include:

- Written approval of the study protocol with all amendments by Ethic Committee
- All source documents and results of investigations
- Patient informed consent forms (with protocol number and study name)
- Any other documentation relevant to the study.

## **10 STATISTICS**

### **Statistical Analysis**

#### **10.1 General methods of analysis**

Statistical analysis will be conducted under the supervision of a responsible biostatistician. The details of statistical analysis will be provided in the statistical analysis plan in accordance with the GCP requirements and other relevant requirements and laws. The statistical analysis plan will be finalized before the data lock point. All deviations from the final statistical plan version will be justified in the final program report.

The results will be combined for the complete study sample. Two-sided levels of significance and confidence intervals will be calculated. The significance of differences will be calculated for two-sided tests, with a critical significance level of 0.05.

For parameters of interval scale type, the following will be calculated: the arithmetic mean (95% confidence interval for the mean), standard deviation, median, 25th and 75th percentiles. For parameters of ordinal scale type, median, 25th and 75th percentiles will be calculated. For parameters of nominal scale type, frequency categories and confidence intervals for the frequencies (modified Wald method) will be calculated. If the assumptions made during the preliminary study planning are found to be erroneous, the analysis methods will be modified to conduct a more suitable analysis. The result of the primary endpoint analysis will be presented as an absolute number and proportion (%) of patients with target BP (<140/90 mm Hg) achieved at visit V4.

Statistical analysis will be carried out using SPSS/PASW Statistics software package (version 18), SPSS Inc., Chicago, Illinois, USA.

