	
Changes in mean telomerase activity at visit 4 versus baseline level (visit 1 in comparison between the groups).
 
Changes in mean pulse wave velocity (PWV) at visit 4 versus baseline level (visit 1) and in comparison between the groups.
 
Changes in mean intima-media thickness (IMT) at visit 4 in comparison between the groups.
 
The efficacy of the investigated treatment is estimated based on whether target blood pressure (<140/90 mm Hg) at visits V2, V3 and V4 is reached.
 
Safety Analysis:
 
Adverse events (AEs) are recorded at every visit. Analysis of adverse events and serious adverse events is conducted to determine the total number of AEs, the total number of patients with adverse events, the number of treatment-related adverse events, the number of AEs associated with product discontinuation and the number of voluntary withdrawal of informed consent.
 
Rate and severity of all adverse events and drug-related adverse events (i.e., at least “possibly” associated with the studied product) will be summarized by organ systems. Data on the product withdrawal due to adverse events will be summarized in tables.
 
Statistical methods:
 
Statistical analysis will be conducted under the supervision of a responsible biostatistician. The details of statistical analysis will be provided in the statistical analysis plan in accordance with the GCP requirements and other relevant requirements and laws. The statistical analysis plan will be finalized before the data lock point. All deviations from the final statistical plan version will be justified in the final program report.
 
The results will be combined for the complete study sample. Two-sided levels of significance and confidence intervals will be calculated. The significance of differences will be calculated for two-sided tests, with a critical significance level of 0.05.
 
For parameters of interval scale type, the following will be calculated: the arithmetic mean (95% confidence interval for the mean), standard deviation, median, 25th and 75th percentiles. For parameters of ordinal scale type, median, 25th and 75th percentiles will be calculated. For parameters of nominal scale type, frequency categories and confidence intervals for the frequencies (modified Wald method) will be calculated. If the assumptions made during the preliminary study planning are found to be erroneous, the analysis methods will be modified to conduct a more suitable analysis. The result of the primary endpoint analysis will be presented as an absolute number and

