
	
proportion (%) of patients with target BP (<140/90 mm Hg) achieved at visit V4. Statistical analysis will be carried out using SPSS / PASW Statistics software package (version 18), SPSS Inc., Chicago, Illinois, USA.
 
Rationale for sample size As this is an explorative study with open design no formal sample size calculation was performed. The focus of the study is to obtain scientific data for a publication and taking into account a reason of feasibility of enrollment to timelines and screening of 300 patients per year in assumption that ratio of screened / enrolled patients is approximately 3 to 1 so it is expected that not less than 100 patients but no more than 114 patients will be enrolled in the study. According to this approach the total sample size is chosen 114 subjects.

--	------------------------------------------------------------------------------------------------------------------------------------------------------------------------------------------------------------------------------------------------------------------------------------------------------------------------------------------------------------------------------------------------------------------------------------------------------------------------------------------------------------------------------------------------------------------------------------------------------------------------------------------------------------------------------------------------------------------------------------------------------------------------------------------------------------------------------------------------------

LIST OF ABBREVIATIONS AND DEFINITION OF TERMS

ACEI - angiotensin-converting enzyme inhibitor

AE - adverse event

ALT - alanine aminotransferase

AR - adverse reaction

AST - aspartate aminotransferase

BB - beta-blockers

BMD - bone mass density

BMD - bone mineral density

BP - blood pressure

CHD - coronary heart disease

CRF - case report form

CTX - collagen type 1 C-telopeptide

CVD - cardiovascular disease

DBP - diastolic blood pressure

ECG - electrocardiogram

HCF - health care facility

HR - heart rate

HTN - hypertension

IMT - intima-media thickness

OC - osteocalcin

OPG - osteoprotegerin

PWV - pulse wave velocity

RANKL - Receptor activator of nuclear factor kappa-B ligand

SAE - serious adverse event

SBP - systolic blood pressure

TIA - transient ischemic attack

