## **2. PROGRAM OBJECTIVES**

**2.1 Primary objective:** To investigate the effect of moxonidine versus bisoprolol on collagen type 1 C-telopeptide in postmenopausal female patients with arterial hypertension and osteopenia.

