### **3.10 Study endpoints**

#### **Primary endpoint:**

- Changes in mean values of the bone resorption marker (collagen type 1 C-telopeptide) at the end of the study (V4) from the baseline (V1) in comparison between the groups.

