#### **Secondary Endpoints:**

- To assess mean values of osteocalcin at visit 4 versus baseline level (visit 1) and to compare the values between the groups
- To assess mean values of the receptor activator of nuclear factor kappa-B ligand (RANKL) at visit 4 versus baseline level (visit 1) and to compare the values between the groups
- To assess mean values of BMD at visit 4 versus baseline level (visit 1) using control dual-energy X-ray absorptiometry and to compare the results between the groups
- To assess mean telomerase activity at visit 4 versus baseline level (visit 1) and to compare the values between the groups
- To assess mean pulse wave velocity (PWV) at visit 4 versus baseline level (visit 1) and to compare the values between the groups
- To assess mean intima-media thickness (IMT) at visit 4 versus baseline level (visit 1) and to compare the values between the groups
- To estimate the proportion (%) of patients who achieved target blood pressure <140/90 mmHg at the visit 2 (Week 8), 3 (Week 24) and 4(Week 48) and according to the patient's diary.

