### **6.2 Secondary endpoints efficacy criteria:**

1. Changes in mean values of the bone synthesis marker (osteocalcin) at the end of the study (V4) from the baseline (V1) and to compare the values between the groups.
2. Changes in mean values of the receptor activator of nuclear factor kappa-B ligand (RANKL) at visit 4 versus baseline level (visit 1) and to compare the values between the groups

3. Changes in mean values of BMD at visit 4 versus baseline level (visit 1) using control dual-energy X-ray absorptiometry and to compare the results between the groups
4. Changes in mean values of telomerase activity at visit 4 versus baseline level (visit 1) and to compare the values between the groups
5. Changes in mean values of pulse wave velocity (PWV) at visit 4 versus baseline level (visit 1) and to compare the values between the groups
6. Changes in mean values of intima-media thickness (IMT) at visit 4 versus baseline level (visit 1) and to compare the values between the groups
7. Proportion of the treatment responders (defined as the proportion (%) of patients who achieved target blood pressure <140/90 mmHg) after 8 and 48 weeks of the investigated treatment (V2, V3 and V4) and to compare the values between the groups.

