**The main indicator of the treatment efficiency:**

Changes in mean values of the bone resorption marker (collagen type 1 C-telopeptide) at the end of the study (V4) from the baseline (V1) in comparison between the groups.

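### Section 10.1 and the synopsis present the primary endpoint result as the percentage at target BP, although the primary endpoint is the change in CTX

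*Combined protocol and SAP*

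**What the plan says.** Section 10.1 (General methods of analysis) closes its paragraph on summary statistics with: "The result of the primary endpoint analysis will be presented as an absolute number and proportion (%) of patients with target BP", the target being below 140/90 mmHg at V4. The Statistical methods part of the synopsis has the same sentence, broken across two table cells: "The result of the primary endpoint analysis will be presented as an absolute number and" and then "proportion (%) of patients with target BP".

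The rest of the document names a different primary variable. Section 2.1 gives the primary objective as "To investigate the effect of moxonidine versus bisoprolol on collagen type 1 C-telopeptide". Section 3.10 defines the primary endpoint as "Changes in mean values of the bone resorption marker (collagen type 1 C-telopeptide) at the end of the study (V4) from the baseline (V1"), compared between the groups. The synopsis and Section 6.1 repeat that definition, and Section 10.3 gives it again as the main indicator of efficacy.

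Target BP appears as a secondary endpoint. Section 3.10 lists it last among the secondaries: "To estimate the proportion (%) of patients who achieved target blood pressure <140/90 mmHg". Section 6.2, item 7, has it as "Proportion of the treatment responders (defined as the proportion (%) of patients who achieved target blood pressure <140/90 mmHg").

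**The concern.** The sentence cannot be read as a way of presenting CTX. It names another variable (blood pressure) and another type of outcome (a binary status at one visit, not a change in a continuous marker). If the report follows it, the result labelled primary will be a responder percentage that says nothing about bone resorption, which is the question the trial was set up to answer. Treatment is also titrated towards the same BP target, with perindopril or losartan added when needed, so a V4 percentage partly reflects the titration and add-on steps.

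No other sentence is specific to how the primary result will be presented, and no test or model for CTX is named anywhere. Nothing more specific therefore overrides it. A report that led with BP could cite the plan in support.

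**Working it through.** The documents give no figure to reproduce. The sample size of 114 rests on feasibility, with no formal calculation, so no power claim depends on either reading. The check is a comparison of every place that defines or reports the primary endpoint.

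| Place | Role given to CTX change | Role given to target BP |
|---|---|---|
| Synopsis, objectives | Primary objective | Not named; antihypertensive efficacy is a secondary objective |
| Synopsis, endpoints | Primary | Secondary, item 7 |
| Section 2.1 | Primary objective | – |
| Section 3.10 | Primary | Secondary |
| Section 6.1 | Primary | – |
| Section 6.2 | – | Secondary, item 7 |
| Section 10.3 | Main indicator (and again among the secondaries) | Secondary |
| Section 10.1 | – | **Presented as the primary result** |
| Synopsis, Statistical methods | – | **Presented as the primary result** |

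**Count.** CTX is the primary objective or endpoint in 6 places: synopsis objectives, synopsis endpoints, and Sections 2.1, 3.10, 6.1 and 10.3. Target BP is in a secondary endpoint list in 4: synopsis endpoints and Sections 3.10, 6.2 and 10.3. It is in no definition of a primary or co-primary endpoint. The conflicting sentence stands in 2 places.

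**Fit with its own paragraph.** Section 10.1 summarises interval-scale variables by the mean with 95% confidence interval, SD, median and quartiles. It summarises nominal variables by frequencies with modified Wald intervals. CTX change belongs to the first rule. A number and percentage at target BP belongs to the second. So the format suits a binary endpoint, and the error lies in calling that endpoint primary.

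**Possible correction elsewhere.** Section 10.1 defers analysis details to a SAP to be finalised before data lock. A separate SAP could put the sentence right, but nothing in these documents does.

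**Neighbouring wording.** Three other statements add to the ambiguity:

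- The synopsis judges treatment efficacy by whether target BP is reached at V2, V3 and V4, and Section 10.3 bases the evaluation of efficacy at those visits on systolic and diastolic BP.
- The secondary list in Section 10.3 includes CTX, which the same section has just named as the main indicator.
- Section 10.3 ends by promising descriptive statistics, interpreted against historical control. That sits poorly with its own between-group CTX comparison and with the two-sided 0.05 tests in Section 10.1.

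**The case against.** The strongest reply is that this is an editorial slip with little consequence. Endpoint status is fixed consistently elsewhere, and the sentence concerns presentation without redefining the endpoint. The study describes itself as explorative and has no power calculation to upset, and a SAP is still to come. That it would lead anyone to headline BP is conjecture. All of this bears on severity, and it is right that a careful reader would not be misled about which endpoint is primary. It does not remove the contradiction. An explorative trial that names one primary endpoint, tests at two-sided 0.05 and is meant for publication still needs its reporting rule to name the right variable.

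A second objection is that the sentence is not a lone outlier, given the BP-centred efficacy wording and the repeated listing of CTX in Section 10.3. That is correct. It widens the clean-up needed, and none of that wording makes BP a primary endpoint.

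A third is that baseline adjustment goes further than the contradiction requires. This also stands. Reconciling the text needs only the correct variable and the between-group comparison. Adjustment for V1 CTX is a recommendation, made because no analysis model for CTX is stated.

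Finally, the descriptive and historical-control wording in Section 10.3 is a separate weakness. It is mentioned because it touches the same primary result, and the main conclusion does not depend on it.

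**Conclusion.** The concern holds. The sentence in Section 10.1 and the synopsis assigns the primary result to a secondary, binary BP outcome, against a primary objective and endpoint that are CTX throughout. What changes is which outcome is reported as primary: a between-group difference in CTX change, or a percentage at target BP at V4. The size of the effect on any estimate cannot be stated, because these are different variables. The conclusion rests on the text alone and assumes that no separate SAP has already corrected the sentence. It should be fixed before data lock. It is not a fatal flaw, since the intended primary endpoint can be recovered from the rest of the plan.

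**What to change.** 1. In Section 10.1 and in the synopsis, replace the sentence with: *The primary result is the between-group difference (moxonidine minus bisoprolol) in change in CTX from V1 to V4, with two-sided 95% confidence interval and p-value, adjusted for V1 CTX (for example by analysis of covariance, on a transformed scale if the distribution requires it).* If the sponsor prefers not to adjust, the sentence should still name the CTX difference and its interval, and the test to be used.
2. Report the number and percentage at target BP at V4 under secondary endpoint 7.
3. At the end of Section 10.3 add: *The primary CTX endpoint is compared between the randomised groups as in Section 10.1; published data are used for context only.*
4. For consistency, remove CTX from the secondary list in Section 10.3, and describe the BP-based evaluation there and in the synopsis as antihypertensive efficacy.

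The cost is wording in Sections 10.1 and 10.3 and the synopsis, plus one analysis choice if baseline adjustment is adopted. V1 CTX is already collected, so no new data, visits or patients are needed.
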